Stress-related processes, parenting quality, and maternal cognitive resources at ages 1, 2, and 3. To further assess the family stress pathway, information on maternal stress, mental health and interactions with children will be collected at child ages 1 and 2. Survey measures will assess family stress, chaos in the home, parenting beliefs and maternal symptoms of depression and anxiety. The videotaped free play and clean-up task at child age 2 will be coded for parental warmth and harshness. As a measure of maternal sensitivity, we will analyze mother and child synchrony in baseline cortisol levels, as well as in stress reactivity/recovery during the scary mask presentation described above (as the mother will observe her child's distress during the task). Higher mother-child synchrony is linked to better attachment, language, and socioemotional competence,¹⁵² and lower SES dyads tend to have reduced synchrony relative to higher SES counterparts.¹⁵³ The NIH Toolbox Flanker test will be administered to mothers at child ages 2 and 3 to measure maternal cognitive resources (executive functioning, or "bandwidth"). Administrative data will enable us to track child welfare reports. Finally, data on preventive health care visits, including well-child and dental visits, will be collected via parent interview.

Demographic characteristics. Baseline demographic measures, listed in Appendix 5, will be used to improve the precision of our experimental impact estimates and, in some cases, enable us to examine whether and how impacts vary by some of these key baseline characteristics.

Long-term Follow-up. Although our 5-year window of research will enable us to collect data through age 3 and run basic impact and some moderation analyses, we will continue to engage in project activities beyond the end of our grant period. Since subject consent forms cover administrative data generated after age 3, we plan to secure additional funding for subsequent collection and analyses of administrative data, including school records of target children and their siblings. The large number of family- and child-based measures collected in our age 2 home visits will be available for analysis 18 months prior to the end of our grant period, and will inform subsequent data collection strategies including the possibility of MRI-based measures of regional brain structure and function when the children are old enough to be assessed with this technique.

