EEG: resting brain function (power , an index of cortical activation reflecting synchronous post-synaptic currents within a local neuronal population, and coherence , a measure reflecting synchronization of oscillatory EEG activity between electrode sites, serving as a putative measure of functional connectivity)	Marshall et al 2002 ¹³²	About 10 minutes	n/a	3
ERP: language (comparison of brain activity to known words vs. unknown words)	Zangl & Mills (2007) ¹⁷⁵	About 5 minutes	n/a	3
ERP: memory (comparison of brain activity to previously-seen vs. novel faces)	Nelson & Collins (1991) ¹³⁵	About 5 minutes	n/a	3
Health and Development				
Well-baby visits, illness, diagnoses and medications, injuries	MetroBaby ¹⁷⁶	About 5 minutes	n/a	1, 2, 3
Developmental milestones	Ages and Stages Questionnaire (ASQ) ¹⁷⁷	10-15 minutes	Sensitivity .86 Specificity .85	1,2,3
Body Mass Index (BMI)	CDC	About 2 minutes	n/a	3
School Achievement				
School test scores for target children and siblings	Administrative data			ages 5+

^a Source of item indicates a recent survey or study with comparable samples that administered the item. When not available, source indicates the primary authors of the scale or item. MetroBaby=NYU Center for Research on Culture, Development, and Education Birth Cohort Study, see www.steinhardt.nyu.edu/crcde/projects/childhood; NIH Toolbox= Northwestern University and NIH, see www.nihtoolbox.org; NCS=National Children's Study, see <http://www.nationalchildrensstudy.gov/research/workshops/Pages/U-Minnesota-formative-ncs-research-day-2011.pdf>

^b 1 = age 1 phone interview, 2 = age 2 home visit, 3 = age 3 lab visit; administrative data are gathered continuously and will be accessed shortly before they will be analyzed.

Appendix 5: Measures of Maternal and Family Processes and Characteristics (Note: not all of these measures are preregistered)

Measure description	Item source ^a	Wave ^b
Household Economic Behavior		
Household income: total earnings, total from social assistance and related programs	MTO ¹⁷⁸ and admin data	H, 1,2,3
Household size: roster of every person residing in the household, relationship to the infant, age, sex	MTO ¹⁷⁸	H, 1,2,3
Indicators of economic stress: utility cutoffs, eviction, missed payments, untreated health conditions	MTO ¹⁷⁸	H, 1, 2, 3
Food insufficiency: less than desired amount of food, type of food, skipped meals	MTO ¹⁷⁸	H, 1, 2, 3

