Household expenditures: rent/mortgage, utilities, transportation costs, alcohol, drugs, cigarettes	MetroBaby ¹⁷⁶	H, 1, 2, 3
Net worth: formal and informal debt, any assets/savings	MTO ¹⁷⁸	H, 3
Housing and Neighborhoods		
Perceptions of neighborhood safety: safety, victimization	MTO ¹⁷⁸	H, 1, 2
Neighborhood poverty: Census data on percent poor in the neighborhood	Census	H, 1, 2, 3
Housing quality: crowding/number of rooms, type of housing, housing problems	MTO ¹⁷⁸	1, 2, 3
Residential mobility: number of moves in recent past, whether voluntary/involuntary	MTO ¹⁷⁸	1, 2, 3
Parental Employment		
Parental work histories and schedules: total hours (full or part time), number of jobs, days worked, regularity of work schedule	MetroBaby, ¹⁷⁶ MTO, ¹⁷⁸ admin data	H, 1, 2, 3
Nonparental Care		
Nonparental care experiences: number and type of providers, hours in care, regularity of care, qualities of care	NSECE	1, 2, 3
Maternal Relationships		
Mother's romantic relationships: marital status, relationship quality with biological father and/or other romantic partner, presence of domestic violence	MetroBaby, ¹⁷⁶ CDC	H, 1, 2, 3
Home Environment		
Child-related enrichment expenditures: children's books and toys, out-of-pocket nonparental care	MetroBaby ¹⁷⁶	1,2, 3
Parent-child interaction and environment: Infant/Toddler HOME Inventory (stimulating toys and activities, home organization)	Caldwell & Bradley ¹⁷⁹	2
Parent-child language: mean length of utterance, types and tokens from videotaped interaction (free play and clean-up task)	Matas et al. ¹⁸⁰	2
Chaos in the home: Home Environment Chaos Scale	Evans ¹⁸¹	H, 1, 2, 3

Parental Stress		
Family stress: parenting-related stressors	Fragile Families ¹⁸²	1, 2, 3
General stress: Perceived Daily Stress Scale	Cohen & Williamson ¹⁸³	1, 2, 3
Maternal hair cortisol: index of chronic stress	1 measure ^{138,65,141,142}	2
Maternal salivary cortisol: index of acute stress	3 measures ^{100,133-136,184-193}	2
Maternal cognitive resources (“bandwidth”): Flanker Inhibitory Control and Attention Test	NIH Toolbox ¹⁶⁸	2, 3
Child protective services: maltreatment investigations and substantiations	Admin data	H, 1, 2, 3
Maternal Health		
Physical health: general health, pregnancy, contraception	MetroBaby ¹⁷⁶	H, 1, 2, 3
Mental health: depression, anxiety	PHQ-9 ¹⁹⁴ , Beck ¹⁹⁵	H, 1, 2, 3
Child Stress		
Child hair cortisol: index of chronic stress	1 measure ^{66,140,141}	2

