Our basic empirical approach will use the survey and neuroscience data to compare the pooled cross-city \$333/month and \$20/month groups on a wide range of family process and child outcome measures. Because of random assignment, the low cash gift group average outcomes enable us to identify the average outcomes corresponding to the counterfactual state that would have occurred for individuals in the high cash gift group if they had not been offered the additional \$313/month income supplement. Therefore, differences in outcomes for the high compared with the low group (after random assignment) can be interpreted as estimates of causal treatment effects of the \$313/month higher income (regardless of whether treatment-group participants actually expend all of the funds.) These are commonly known as intent-to-treat effects.

Estimation strategy. We illustrate our approach to estimation in a simple regression framework. The “Intent-To-Treat effect” (ITT) is captured by the estimate of the coefficient π_1 in a regression of some child or family process outcome (Y) on a dichotomous indicator for assignment (Z) to the high payment group as in (1).

$$(1) Y = Z\pi_1 + X\beta_1 + \varepsilon_1$$

We have experienced extremely low rates of “non-compliance” with the offer of cash gifts paid via the debit cards, with less than 10 of the 1,000 participants never having charged anything on their debit cards. We will adjust standard errors using robust variance estimation techniques (Cameron et al. 2008). We will estimate (1) without and then with baseline demographic child and family characteristics (X) to improve the precision of our estimates by accounting for residual variation.

Baseline measures, all gathered prior to random assignment, have been checked for adequate variation and sufficient independence from other baseline measures. They include: dummy variables for three of the four sites; mother’s age, completed schooling, household income, net worth, general health, mental health, race and Hispanic ethnicity, marital status, number of adults in the mother’s household, number of other children born to the mother, whether the mother smoked or drank alcohol during pregnancy and whether the father is currently living with the mother; and child’s sex, birth weight, gestational age at birth, and birth order.

Analysis Plan for Phase 1

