"Take-up" of the cash gifts is virtually universal, with fewer than six families never having used their debit cards by child age 3. We will adjust standard errors using robust variance estimation techniques (Cameron et al. 2008). We will estimate (1) without and then with baseline demographic child and family characteristics (X) to improve the precision of our estimates by accounting for residual variation. These baseline measures, all gathered prior to random assignment, have been checked for adequate variation and sufficient independence from other baseline measures. They include: dummy variables for three of the four sites; mother's age, completed schooling, household income, net worth, general health, mental health, race and Hispanic ethnicity, marital status, number of adults in the mother's household, number of other children born to the mother, whether the mother smoked or drank alcohol during pregnancy and whether the father is currently living with the mother; and child's sex, birth weight, gestational age at birth, birth order and interview/assessor ID. For child outcomes we also control for child's age in months at the time of the survey/assessment.

Analysis Plan for Phase 2

We will apply our regression estimation strategy to the assessment-based measures of cognitive, language, self-regulation, and socio-emotional functioning and EEG measures of brain activity gathered at ages 6 and 8. To investigate family process impacts, we will apply our estimation strategy to maternal and family measures gathered at child ages 6 and 8.

Attrition. The greatest threat to internal validity is bias from sample attrition overall, within site, and differential attrition rates by treatment status overall and within site. We will carefully track response rates by site, by treatment status across sites, and then treatment status within site. Response rates were very high for the ages 1-3 data collections and varied across measures at age 4. Of the original 1,000 recruited participants, we secured interviews with 931 at age 1, 922 at age 2, and 922 again at age 3. By age 4, 5 mothers and 5 children had died and we gathered information on between $n=634$ (for child EEG) to $n=882$ (for maternal reports of behavior problems) of the remaining 990 families.

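### The covariate list leaves out the planned hospital-baseline measures of economic stress and food insufficiency (and of tract poverty and work history), so the outcomes built on them are not adjusted for their own baseline

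*SAP*

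**What the plan says.** **Planned at baseline.** Protocol Appendix 5 assigns these measures to wave H (hospital at birth) as well as to later waves: "Indicators of economic stress: utility cutoffs, eviction, missed payments, untreated health conditions"; "Food insufficiency: less than desired amount of food, type of food, skipped meals"; "Neighborhood poverty: Census data on percent poor in the neighborhood"; and parental work histories and schedules. The Protocol's paragraph on demographic characteristics says that the baseline demographic measures listed in that appendix "will be used to improve the precision of our experimental impact estimates".

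**Covariates.** The Estimation strategy sections of SAP Phases 1 and 2 fit the model without and then with X, the latter "to improve the precision of our estimates by accounting for residual variation". The Phase 1 list begins "They include: dummy variables for three of the four sites; mother’s age, completed schooling, household income, net worth, general health, mental health". Phase 2 repeats it, including "completed schooling, household income, net worth, general health, mental health, race and Hispanic ethnicity, marital status" and "number of adults in the mother's household, number of other children born to the mother", and adds interviewer/assessor and, for child outcomes, child age. The July 2025 addenda add only child age and interviewer/assessor. None of the four measures above appears.

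**Stated screen.** Both phases say that the baseline measures were checked for variation and for independence from one another. No result is reported for the hardship items.

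**Outcomes.** In Appendix Table 10 the Household Economic Hardship cluster has these primary outcomes: the economic-stress index (ages 1, 2, 3, 4, 6, 8), household poverty rate (same ages), the food-insecurity index (ages 1-4) and a single emergency-expense item (ages 6, 8). Neighborhood poverty, labor-market participation and earnings are secondary.

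**Weights.** The treatment and non-response weights in the Phase 2 Attrition section are built from all baseline control variables and the child's age.

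**The concern.** X is there for precision, and the pre-randomization value of the same construct is often among the best predictors of an outcome. The list already does this for some outcomes: baseline mental health serves depression and anxiety, and baseline general health serves global health. It does not do it for the economic-stress index, a primary outcome that lies close to the intervention and also faces familywise adjustment within its cluster. Baseline income and net worth stand in only partly. Eligibility caps prior-year income at the poverty line, so its range is restricted, and whether a family missed rent or lost utilities is different information.

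Two things are at stake: wider intervals than necessary on these outcomes, and weights for attrition that ignore baseline hardship. The SAP calls attrition bias the greatest threat to internal validity.

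**Working it through.** **1. Which outcomes have a planned baseline that X omits?**

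| Outcome (Table 10) | Status | Planned wave-H counterpart | In X? |
|---|---|---|---|
| Economic-stress index | Primary, ages 1-4, 6, 8 | Stress indicators; food insufficiency | No |
| Food-insecurity index | Primary, ages 1-4 | Food insufficiency | No |
| Household poverty rate | Primary, ages 1-4, 6, 8 | Income and household size | Main ingredients yes |
| Emergency-expense item | Primary, ages 6, 8 | None listed | Not applicable |
| Neighborhood poverty | Secondary, ages 1-4, 6, 8 | Tract poverty | No |
| Labor-market participation, earnings | Secondary, ages 4, 6, 8 | Work history | No |

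The gap therefore touches two of three primary hardship outcomes at ages 1-4 and one of three at ages 6/8.

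**2. How well do the items match?** At ages 6/8, five of the six index items have a planned baseline counterpart: missed rent, missed utility payment, shut-off, eviction and going hungry. Free food does not. At ages 1-3, five of nine match: missed rent, missed utilities, shut-off, eviction and unmet care. Worry, overspending, rainy-day funds and ability to cover expenses do not match. Unmet care is dropped at age 4.

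**3. Reproduce the plan's figure.** Phase 2 power inputs: n=800 split 320/480, 80% power, α=.05, no covariates.

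Detectable effect = (z_α + z_power) × √(1/320 + 1/480), and the square root is .0722.
- One-tailed: (1.645 + .842) × .0722 = .179 (stated .18).
- Two-tailed: (1.960 + .842) × .0722 = .202 (stated .20).

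Power at .18 one-tailed is 80.2%. The plan's figures hold.

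**4. Gain over the existing X.** No correlations are given, so these are assumptions:
- r: correlation of the outcome with its own baseline, 0.2 to 0.5.
- a: multiple correlation of the outcome with X, 0.3 or 0.4 (9% or 16% of variance).
- b: correlation of baseline hardship with the X-based predictor, 0.3 to 0.5.

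R² with X alone = a². R² with the baseline added = (r² + a² − 2rab)/(1 − b²). Power = Φ(.18/se − 1.645), with se = √((1 − R²)/(800 × .4 × .6)).

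Worked case, r=.3, a=.3, b=.4: R² = (.09 + .09 − .072)/.84 = .129; se = √(.871/192) = .0674; power = Φ(2.672 − 1.645) = 84.8%. With X alone, R² = .09, se = .0688 and power is 83.4%. The gain is 1.4 points.

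| r | a=.3, b=.3 | a=.3, b=.4 | a=.4, b=.5 |
|---|---|---|---|
| X alone | 83.4% | 83.4% | 85.9% |
| 0.2 | +0.5 | +0.3 | 0.0 |
| 0.3 | +1.7 | +1.4 | +0.5 |
| 0.4 | +3.8 | +3.4 | +1.9 |
| 0.5 | +6.7 | +6.2 | +4.3 |

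Gains are in percentage points, taken before rounding. Two-tailed at .18 sd and r=0.5, power goes from 74.4% to 82.7-83.4% (a=.3) or from 77.7% to 83.6% (a=.4), a gain of 6 to 9 points. That case is the relevant one for participation and earnings, which have no directional hypothesis. All figures are for a single test, before the cluster adjustment.

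**The case against.** The strongest reply has four parts.

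*Collection is not confirmed.* Appendix 5 is a plan. The SAP mentions only a 30-minute baseline interview and does not say that hardship or work items were asked. Its covariates include gestational age, which Appendix 5 does not list, so the appendix is not the final instrument. This stands, and the fix must read where collected.

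*One common X is a legitimate choice.* It limits outcome-by-outcome covariate picking, and a screen is stated. This stands in part. A common list is defensible, but the screen reports nothing for these items, and independence from other baseline variables is not the criterion by which a lagged outcome earns its place. That the list is closed is also an inference, since it opens with an including phrase, although it reads as the preregistered set.

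*The gain may be small.* Items match imperfectly, six to eight years pass, and income, net worth and mental health already carry part of the signal. Sample size may also exceed 800: one maternal-report measure reached 882 at age 4, where unadjusted one-tailed power at .18 sd would already be 83.5%. This stands.

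*Changing the Phase 1 list now would be post hoc.* Age-4 data are in, and the Phase 2 EEG section already refers to age-4 results. This stands.

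A reader might also infer that every primary hardship outcome lacks its baseline. That is not so. Income, adults and other children are in X, and baseline poverty status is near constant by eligibility, so household poverty rate is covered. The emergency-expense item has no hospital counterpart, and food insecurity is not registered at ages 6/8.

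**Conclusion.** The omission is real, narrow and cheap to repair. It affects the economic-stress index at all its ages, the food-insecurity index at ages 1-4, and the secondary tract-poverty, work and earnings outcomes.

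Its size rests wholly on assumed correlations: about 0-2 power points at r of 0.2-0.3, 2-4 at 0.4 and 4-7 at 0.5 (n=800, .18 sd, one-tailed, over the existing X). A reader might take the gain at r=0.5 to be 9 points (80.2% to 89.2%), but that compares with a model containing no covariates, which is not the alternative here.

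Nor do the documents support a reading of bias. Randomization protects the full-sample intent-to-treat contrast with or without these covariates, and the plan's power statement assumes none. The link to attrition is indirect. The weights inherit the same gap, and whether baseline hardship predicts loss to follow-up is plausible but not shown. Multiple imputation, which draws on all available data, covers part of it.

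This is a cheap improvement, not a correction of an error in the plan.

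**What to change.** In the Phase 2 Estimation strategy, for ages 6 and 8, add wording such as: *For the economic-stress index, X also includes the baseline (hospital) count of economic-stress indicators and food-insufficiency items, where collected; for neighborhood poverty, the baseline tract poverty rate; for labor-market participation and earnings, baseline maternal work status. A missing indicator is used where the baseline value is absent.*

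Include the same variables in the treatment and non-response weighting models. If any was not collected, or failed the variation or independence check, say so instead.

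Date the amendment before the age-6 and age-8 arm comparisons, and keep reporting the unadjusted and current-X models. Leave the Phase 1 list as it is. For ages 1-4, run the added adjustment only as a labelled post hoc sensitivity analysis.

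The cost is about one degree of freedom per added variable and a second amendment to the covariate list. No new data collection is needed if the hospital items were asked as planned.
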